1. INTRODUCTION

The common cold is part of life, with most adults having 2-3 symptomatic infections per year, and children having a much higher incidence [Simasek, 2007]. Over \$3 billion are spent on over-the-counter (OTC) cough and cold remedies each year in the US [Boujaoude and Pratter, 2010]. Treatment options for the common cold focus on symptom control. For example, intranasal or oral decongestants are effective to improve nasal patency and thus relieve congestion [Sperber, 1989], first generation antihistamines reduce sneezing (Gwaltney 1997), ipratropium reduces rhinorrhea [Hayden 1996] and non-steroidal anti-inflammatory drugs (NSAIDS) may reduce fever and sore throat [Sperber, 1992]. Antitussives and mucolytics are often used to ameliorate cough and promote expectoration [Singh, 2013].

As the common cold is manifest through a plethora of symptoms, not all of which are displayed by each sufferer, there is a need for treatment options which are not specifically symptom related. Agents such as zinc, used as a preventative, given within 24 hours of symptom onset, have been shown to reduce the severity and duration of symptoms [Singh, 2013]. Various nasal sprays that do not contain pharmacologically active ingredients are available as physical barriers to prevent viruses interacting with nasal epithelium cells but little clinical data exist to support a benefit [Hull, 2007].

The pathophysiological processes that cause symptoms of the common cold continue to be explored. The fundamental premise was established in 1982 when it was proposed that these symptoms are mediated through the release of inflammatory substances by the host in response to infection and that direct viral cytopathology is of lesser importance [Turner 1982]. More recently confirmatory evidence of the role of the immune response to symptomatology has been demonstrated for rhinoviruses, which are the predominant cause of the common cold [Proud, 2008]. Once activated the humoral immune response continues irrespective of viral presence [Kennedy, 2012] so the target of minimizing the symptom complex must concentrate on containing the immune system responses while not interfering with the required antiviral activity. In addition to the barrier approach cited above [Hull, 2007], prevention of viral attachment to nasal epithelial cells via the Intercellular Adhesion Molecule 1 (ICAM-1) receptor, the mechanism by which the virus gains access to the cell to allow replication, has been explored. Tremacamara, a recombinant soluble ICAM-1, was shown to be effective in reducing the symptoms of experimental common colds [Turner, 1999]. A novel approach to minimizing an upper respiratory tract infection is to combine a barrier effect with an activity which prevents rhinovirus from binding to ICAM-1 receptors.

1146A contains carbomer 980, one of a series of anionic, synthetic, high molecular weight, non-linear polymers of acrylic acid [ACT, 1982]. CCI

Document Name	CCI	Protocol B_Final_Amendment 4_Clean_QA Review		
Type	Version	Document Identifier	Effective Date	
elido_clinical_doc	1.0; CURRENT; Most-Recent; Effective	090032d580d43d4b	19-May-2017 09:57:58	
Reason For Issue	Auto Issue			

CCI

Carbomers inhibit human rhinovirus replication by a dual mode of action. First, above concentrations of 0.1% w/w carbomer 980 forms a viscous gel, which acts as a physical barrier. Second, carbomers are anionic and are believed to readily associate with the cationic binding sites on HRV which prevents viral interactions with the nasal epithelial cells via the cell surface receptors. Therefore, by preventing interaction with the cell surface receptors, the virus is prevented from entering the cell [Kennedy, 2012].

Carbomer 980 and 940 are used in ophthalmics, topicals, drugs, cosmetics, nasal moisturizing gel (Ocean Nasal Moisturizer Gel®- concentration unknown) and toothpaste [Lubrizol, 2010] and are generally regarded as safe.

2. OBJECTIVES AND ENDPOINTS

Objectives	Endpoints
Primary	

 To assess the efficacy of 1146A in reducing the severity of nasal symptoms on days 1-4, using the average nasal symptom score, compared to placebo in adult subjects with the common cold 	
 Average nasal symptom score Days 1-4 (ANSS 1-4)
Secondary	
Efficacy	

 To assess the efficacy of 1146A in reducing the severity of nasal symptoms on days 1-7, using the average nasal symptom score, compared to placebo in adult subjects with the common cold 	
 Average nasal symptom score Days 1-7 (ANSS 1-7)

 To assess the efficacy of 1146A in reducing the severity of symptoms on days 1-4 and days 1-7, using the total symptom score, compared to placebo in adult subjects with the common cold 	
 Average total symptom score Days 1-4 (ATSS 1-4) Average total symptom score Days 1-7 (ATSS 1-7)
Safety	

 Adverse events 	
 Spontaneous and solicited adverse events and serious adverse events

Document Name	CCI	Protocol B_Final_Amendment 4_Clean_QA Review		
Type	Version	Document Identifier	Effective Date	
elido_clinical_doc	1.0; CURRENT; Most-Recent; Effective	090032d580d43d4b	19-May-2017 09:57:58	
Reason For Issue	Auto Issue			

Exploratory

- To assess the efficacy of 1146A in reducing the severity of individual symptoms, using the individual symptom score, compared to placebo in adult subjects with the common cold
- Individual & composite total symptom scores (NSS and TSS) Days 1-7

3. STUDY PLAN

3.1. Study Design

Overall Design

This is a multi-center, randomized, parallel-group, double blind, 2-arm, placebo-controlled study to evaluate the efficacy and safety of 1146A (CCI carbomer 980 gel nasal spray) in adult subjects with symptomatic common cold in an outpatient setting.

At Screening (Day 1, Visit 1), subjects with symptoms consistent with symptomatic common cold of ≤48 72 hour duration will provide written informed consent to be enrolled into the study. During this visit, subjects will undergo eligibility screening, which includes: assessment of common cold symptoms and diagnosis by the Investigator; review of demographics, medical and medication history; vital sign assessments (blood pressure, pulse rate, respiratory rate, oral body temperature, height and weight measurements); physical examination; Investigator-led nasal examination; urine pregnancy test (only female subjects of childbearing potential); and urine drug screen.

Only subjects meeting all eligibility criteria including the following symptomatic common cold symptoms will be enrolled into the study:

1. A confirmed common cold diagnosis with symptoms ≤48 72 hours;
2. TSS ≥ 9 (baseline sum of the 8 common cold symptoms described in Section 6.1.7.);
3. Score ≥1 for at least one of the following symptoms: sore throat, runny nose, or blocked nose.

Approximately 300170 eligible subjects (approximately equal numbers of males and females) will be randomized to treatment with 1146A nasal spray or placebo (vehicle, nasal spray) in a 1:1 ratio at multiple sites. All sites should make an effort to enroll approximately equal number of males and females into the study. The study sites will

Document Name	CCI	Protocol B_Final_Amendment 4_Clean_QA Review		
Type	Version	Document Identifier	Effective Date	
elido_clinical_doc	1.0; CURRENT; Most-Recent; Effective	090032d580d43d4b	19-May-2017 09:57:58	
Reason For Issue	Auto Issue			

stratified and randomize eligible subjects using IRT.

Study site personnel will dispense and train subjects on the e-diary and subjects will then perform their baseline self-assessment of common cold symptoms in their e-diary. A nasal swab sample will be taken for possible future virological analysis. An independent site personnel, who will have no other responsibilities during the study, will then instruct subjects on proper use, priming and administration technique of study treatment. Subjects will be instructed to dose for the full seven days irrespective of symptom resolution to avoid inappropriate discontinuation due to misinterpretation of reduced symptomatology as a result of the fluctuation of symptoms that occurs with a common cold. Subjects will also be instructed to change to a new study treatment device every 2 days and to prime the new device prior to the morning dose. The independent site personnel will then dispense the devices and demonstrate how to prime the devices by priming the first device. They will then monitor eligible subjects while the subject administers the first dose of study treatment.

Study treatment will be administered via a nasal spray device (1 dose =3 actuations per nostril, each actuation is 140 μ L). Dosing administration is 3 actuations per nostril per dose, four times a day for 7 days (except for Day 1 where subjects in the 2nd strata will receive 3 doses). Subjects will be instructed to alternate nostrils after each actuation. First administration of study treatment will occur at the study site by independent site personnel supervision that will have no other responsibilities during the study; first dosing can occur any time prior to 13:00.

Subject randomization will be stratified by dosing time on Day 1 by those study subjects receiving first dose of study treatment between the hours of: 8:00-11:00 and those receiving first dose of study treatment between the hours 11:01-13:00. On Day 1, subjects dosing between 8:00-11:00 will dose every 4 hours \pm 30 minutes for 4 doses and subjects dosing between 11:01-13:00 will dose every 4 hours \pm 30 minutes for 3 doses.

On Days 2-7 all subjects will administer their initial morning dose immediately following recording of their common cold symptom assessment at 07:00 \pm 2 hours and the remaining 3 doses every 4 hours \pm 30 minutes.

Dosing times and number of actuations will be recorded in subject's e-diary. Subjects will be instructed not to take any additional cough/cold medications, including but not limited to, prescription, OTC, non-drug/nutritional supplement, or procedures throughout the study. Subjects will be instructed to use acetaminophen/paracetamol over other OTC medications, but should try to avoid use if possible. See Section 3.2 and 4.2 for more detail.

Document Name	CCI	Protocol B_Final_Amendment 4_Clean_QA Review		
Type	Version	Document Identifier	Effective Date	
elido_clinical_doc	1.0; CURRENT; Most-Recent; Effective	090032d580d43d4b	19-May-2017 09:57:58	
Reason For Issue	Auto Issue			

Subjects will self-evaluate the severity of the following common cold signs/symptoms before each dose and record their assessment in the e-diary: headache, muscle ache, chills, sore throat, blocked nose, runny nose, cough, and sneezing. Subjects will assess symptom severity on a 4-point scale (0=none, 1=mild, 2=moderate, 3=severe) at baseline and 4 times a day (except for Day 1 where subjects in the 2nd strata will receive 3 doses) through Day 7 immediately prior to each dose of nasal spray and record the scores in the e-diary. Safety will be assessed by occurrence of adverse events.

Upon awakening on the morning of Day 8, subjects will complete a self-assessment of common cold symptoms in the e-diary. Subjects will be instructed to return to the study sites on Day 8 (End of study/Visit 2). Nasal examination, physical examination and vital signs will be repeated during this visit. A repeat urine pregnancy test will be performed on all female subjects of child bearing potential. Adverse events and the use of concomitant medications will be recorded by the subjects in e-diaries and monitored by the site personnel throughout the study.

Subjects who discontinue study treatment prior to Day 7 and those who prematurely withdraw from the study for any reason will be instructed to return to the site as soon as possible to undergo all end of study assessments, and then be discharged from the study.

Document Name	CCI	Protocol B_Final_Amendment 4_Clean_QA Review		
Type	Version	Document Identifier	Effective Date	
elido_clinical_doc	1.0; CURRENT; Most-Recent; Effective	090032d580d43d4b	19-May-2017 09:57:58	
Reason For Issue	Auto Issue			

Visit 1 – Screening Visit (Day 1)

The following assessments will be conducted by study site staff:

1. Obtain written informed consent from each subject.
2. Collect demographic data and medical and medication history (previous and concomitant diseases, and pre-study and ongoing concomitant medications, non-drug concomitant treatments/procedures).
3. Instruct and monitor subjects as they perform a self-assessment of common cold symptoms using a 4-point grading scale. This will be recorded in the CRF by site personnel. The Investigator will confirm the common cold diagnosis and only subjects meeting all eligibility criteria and the following criteria will be enrolled into the study (See Section 6.1.7. for more detail):
 - i. A confirmed common cold diagnosis with symptoms <48 72 hours;
 - ii. TSS ≥9 (baseline sum of the 8 common cold symptoms described in Section 6.1.7.);
 - iii. Score ≥1 for at least one of the following symptoms: sore throat, runny nose, or blocked nose.
4. Perform physical examination (including ocular, oropharyngeal and chest examination); vital sign measurements (blood pressure, pulse, respiration rate, oral body temperature, and height and weight measurements).
5. Perform nasal examination by Investigator (for eligibility assessment). See Section 6.1.6. for details.
6. Perform urine drug screen.
7. Perform urine pregnancy test in female subjects of childbearing potential.
8. Eligibility assessment based on inclusion/exclusion criteria.
9. Stratify and randomize eligible subjects using IRT (will also provide subject/kit number).
10. Monitor for SAEs and record any SAEs in CRF.

Document Name	CCI	Protocol B_Final_Amendment 4_Clean_QA Review	
Type	Version	Document Identifier	Effective Date
eido_clinical_doc	1.0; CURRENT; Most-Recent; Effective	090032d580d43d4b	19-May-2017 09:57:58
Reason For Issue	Auto Issue		

Visit 1 – Treatment Phase Visit (Day 1)

1. Dispense and train subject on the e-diary.
2. Subjects perform baseline self-assessment of common cold symptoms in e-diary.
3. A nasal swab sample will be taken for possible future virological analysis.
4. Independent site personnel, who will have no other responsibilities during the study, will instruct subjects on proper use, priming and administration technique of study treatment. Subjects will be instructed to dose for the full seven days irrespective of symptom resolution to avoid inappropriate discontinuation due to misinterpretation of reduced symptomatology as a result of the fluctuation of symptoms that occurs with a common cold. Subjects will also be instructed to change to a new study treatment device every 2 days and to prime the new device prior to the morning dose.
5. Independent site personnel will dispense the devices and demonstrate how to prime the devices by priming the first device.
6. Eligible subject administration of the first dose of study treatment at the site by independent site personnel supervision that will have no other responsibilities during the study, and can occur any time prior to 13:00. Subject randomization will be stratified by dosing time on Day 1 by those study subjects receiving first dose of study treatment between the hours of 8:00-11:00 and those receiving first dose of study treatment between the hours 11:01-13:00. On Day 1, subjects dosing between 8:00-11:00 will dose every 4 hours \pm 30 minutes for 4 doses and subjects dosing between 11:01-13:00 will dose every 4 hours \pm 30 minutes for 3 doses. Dosing time and number of actuations will be recorded in the e-diary.
7. Monitor for SAEs/AEs.
8. Record changes in concomitant medication or non-drug treatments/procedures in the e-diary.

Treatment Continuation and Subject Daily-Conduct (Days 2-7)

The following assessments will be conducted by study subjects every day on Days 2-7:

1. Subject self-assessment of common cold symptoms in e-diary immediately prior to dosing.
2. Subjects will administer their initial morning dose immediately following recording of their common cold symptom assessment at 07:00 \pm 2 hours and the remaining 3 doses every 4 hours \pm 30 minutes. Dosing time and number of actuations will be recorded in the e-diary.
3. Change study treatment devices every 2 days prior to the morning dose.
4. Adverse event recording in the e-diary.
5. Record changes in concomitant medication or non-drug treatments/procedures

Document Name	CCI	Protocol B_Final_Amendment 4_Clean_QA Review		
Type	Version	Document Identifier	Effective Date	
elido_clinical_doc	1.0; CURRENT; Most-Recent; Effective	090032d580d43d4b	19-May-2017 09:57:58	
Reason For Issue	Auto Issue			

in the e-diary.

Visit 2 - End of Study Or Early Termination (Day 8)

1. Subject self-assessment of common cold symptoms in e-diary upon awakening on the morning of Day 8.

The following assessments will be conducted by appropriately trained study site staff:

2. Vital signs measurements (blood pressure, pulse, respiration rate and oral body temperature).
3. Physical examination.
4. Nasal examination by Investigator.
5. Urine pregnancy test in female subjects of childbearing potential).
6. Collection of subject e-diary.
7. Recording of any changes in concomitant medication or non-drug treatments/procedures in the CRF.
8. Monitoring and recording of any adverse events and serious adverse events.
9. Recording of final status of subject and discharge from the study sites at the Investigator's discretion once all study procedures are complete

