3.2. Subject Restrictions

Lifestyle/ Dietary

None

Medications and Treatments

During the entire study (screening – end of study):

- A. Subjects are not permitted use of any medication other than the allocated study treatment and medications to treat chronic, controlled diseases (see Section 4.2, Number 3 for details). In addition, subjects should also refrain from non-drug concomitant treatment or procedures that may interfere with study treatment. In case subjects use any concomitant medication that could interfere with the interpretation of the study results, they will be discontinued from the study.
- B. Intranasal sprays including saline or decongestants within 24 hours.
- C. Intranasal steroids within the past 14 days.
- D. Expectorants, mucolytics, or antitussives within the past 12 hours.
- E. Cough/throat lozenges, menthol chest rub, menthol vaporizers or honey within 6 hours.

Document Name	CCI	Protocol B_Final_Amendment 4_Clean_QA Review		
Type	Version	Document Identifier	Effective Date	
elido_clinical_doc	1.0; CURRENT; Most-Recent; Effective	090032d580d43d4b	19-May-2017 09:57:58	
Reason For Issue	Auto Issue			

F. Non-steroidal anti-inflammatory drug (NSAID), or acetyl salicylic acid within the past 12 hours (immediate release) and 24 hours (sustained release). Acetaminophen/paracetamol may be used occasionally for fever or headache, but subjects should be instructed to try to avoid use if possible.

G. Oral decongestants within 12 hours for short-acting and 24 hours for long-acting.

H. Long acting antihistamines (cetirizine, fexofenadine, hydroxyzine, and loratadine) within 5 days.

I. Short acting antihistamines (e.g., chlorpheniramine, brompheniramine, diphenhydramine), clemastine, long acting forms of chlorpheniramine within 2 days.

J. Asthma medications with the exception of beta-agonists. Subject should be on a stable dose (≥ 7 days) within 24 hours.

K. Herbal OTC medicines for cough/cold (e.g., echinacea, garlic supplements, etc.) for 24 hours.

L. Systemic corticosteroids, immunomodulators within 3 months.

M. Antibiotics within the past 14 days.

N. A flu shot within the past 48 hours.

O. Use of Tamiflu[®] (oseltamivir) or Relenza[®] (zanamivir) within the last 7 days.

P. Other investigational drugs or devices.

Q. Any other treatment the Investigator deems unacceptable for this study.

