9.2.5. Handling of Dropouts and Missing Data

Dropouts will not be replaced and for the primary analysis, missing data after dropout will not be imputed.

For data that is missing at intermediate assessments from subjects who still continue in the study, the fact that these subjects remain in the study and provide data at subsequent assessments supports the assumption that the mechanism for the missing data at these intermediate assessments is unlikely to be related to either their randomized treatment or the condition under study. Therefore, missing common cold symptom scores between two non-missing symptom scores will be imputed by the mean of the last available and the next available symptom score.

In the event that more than 10% of subjects do not complete the first 4 days of treatment (i.e. the period over which the primary endpoint is evaluated) or if there is a differential drop-out rate between the treatment groups, sensitivity analyses using

Document Name	CCI	Protocol B_Final_Amendment 4_Clean_QA Review		
Type	Version	Document Identifier	Effective Date	
eido_clinical_doc	1.0; CURRENT; Most-Recent; Effective	090032d580d43d4b	19-May-2017 09:57:58	
Reason For Issue	Auto Issue			

different imputation methods for data that is missing post-discontinuation will be performed. These sensitivity analyses will be detailed in the SAP.

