Subjects will be instructed not to take any additional cough/cold medications, including but not limited to, prescription, OTC, non-drug/nutritional supplement, or procedures throughout the study. Subjects will be instructed to use acetaminophen/paracetamol over other OTC medications, but should try to avoid use if possible. In the event that a subject uses any additional cough/cold medication (including acetaminophen/paracetamol), its usage (time and reason for use) will be recorded in the e-diary. The primary analysis (modified ITT) will use the recorded cold symptom scores, irrespective of other cough/cold medication usage. The number of subjects using other cough/cold medications and frequency of use will be summarized by treatment group. Additional sensitivity analyses will be performed whereby cold symptom assessments made within 4 hours after the use of any other cough/cold medication are set to missing and various methods used to impute these values. The imputation methods used will (a) reflect the fact that the true cold symptom score, had alternative medication not been used, would have been at least as severe as the cold symptom score prior to the use of the alternative medication, and (b) to ensure the imputed values do not introduce a bias in favor of the test product. Missing data imputations will be applied throughout the assessment period (day 1 to day 8). Further details of the imputation methods will be provided in the SAP.

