4.4.2. Modified Intent-to-Treat (mITT) Population

The mITT population includes subjects who received at least one dose of study medication and have at least one post-baseline efficacy assessment. The mITT will be used for all primary, secondary and exploratory efficacy analyses.

In the event there is a discrepancy between treatment received and randomized treatment, all subjects in the mITT population will be analyzed according to the treatment they were randomized to receive and not according to what they actually received.

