8.1. Primary Efficacy Endpoint

The primary efficacy endpoint is average nasal symptom score on Days 1 to 4 (ANSS₁₋₄). At each assessment, the individual nasal symptom scores will be summed to provide the NSS. On each day, the NSS scores at each assessment (excluding the baseline NSS on Day 1) will be averaged (mean) to provide a daily NSS. A subject's ANSS₁₋₄ is calculated as the mean of these daily NSS across study Days 1 to 4.

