8.1.2. Data Imputation

Dropouts will not be replaced and for the primary analysis, missing data after dropout will not be imputed.

For data that is missing at intermediate assessments from subjects who still continue in the study, the fact that these subjects remain in the study and provide data at subsequent assessments supports the assumption that the mechanism for the missing data at these intermediate assessments is unlikely to be related to either their randomized treatment or the condition under study. Therefore, missing common cold symptom scores between two non-missing symptom scores will be imputed by the mean of the last available and the next available symptom score with the imputed mean rounded up to the next whole number.. Assessment date and time of the imputed common cold symptom scores will not be imputed.

Subjects will be instructed not to take any additional cough/cold medications, including but not limited to, prescription, OTC, non-drug/nutritional supplement, or procedures throughout the study. Subjects will be instructed to use acetaminophen/paracetamol over other OTC medications, but should try to avoid use if possible. In the event that a subject uses any additional cough/cold medication (including acetaminophen/paracetamol), its usage (time and reason for use) will be recorded in the e-diary. The primary analysis (modified ITT) will use the recorded cold symptom scores, irrespective of other cough/cold medication usage. The number of subjects using other cough/cold medications and frequency of use will be summarized by treatment group.

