8.1.3. Sensitivity Analysis for Primary Endpoint

In the event that more than 10% of subjects do not complete the first 4 days of treatment (i.e. the period over which the primary endpoint is evaluated) or if there is a differential drop-out rate between the treatment groups, sensitivity analyses for primary endpoint will be performed using the following methods:

- a. Last observation carried forward (LOCF). If a subject has no further cold assessments after taking an alternative cough/cold medication (including acetaminophen/paracetamol), for subjects in the active group, subsequent symptom scores will be imputed with LOCF+1 (as per the additional sensitivity analysis described below).
- b. Control-based pattern imputation (Ratitch and O'Kelly 2011). The control-based pattern imputation will impute missing scores using available data from placebo subjects for each study day.

Additional sensitivity analyses will be performed whereby cold symptom assessments made within 4 hours after the use of any other cough/cold medication (including acetaminophen/paracetamol) are set to missing and the following imputation algorithm applied:

For subjects in the placebo group, individual symptom scores will be replaced using LOCF; for subjects in the active group, individual symptom scores will be replaced with LOCF+1. If the previous score for an individual symptom is 3 (maximum possible score), then LOCF will be used, as LOCF+1 would result in a value of 4, which is not possible. This imputation algorithm reflects the fact that the true cold symptom score, had alternative medication not been used, would have been at least as severe as the cold symptom score prior to the use of the alternative medication, and it is designed to ensure the imputed values do not introduce a bias in favor of the test product.

The sensitivity analyses will be performed based on the mITT population. Details of sensitivity analyses are provided in Appendix D.

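### Subjects who stop treatment before the end of Day 4 stop supplying symptom scores, so the primary endpoint rests on a shortened average for them, and the control-based check on this is only conditional.

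*Protocol*

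**What the plan says.** **Follow-up after stopping.** Protocol 3.1 (also the synopsis and SAP 3.1) has subjects who stop treatment before Day 7, or who withdraw, return "as soon as possible to undergo all end of study assessments, and then be discharged from the study". Protocol 6.4.6 and the Schedule of Events have the e-diary collected at that visit.

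**Missing data.** Protocol 9.2.5 states that "for the primary analysis, missing data after dropout will not be imputed", and SAP 8.1.2 repeats this: "Dropouts will not be replaced and for the primary analysis, missing data after dropout will not be imputed". Only gaps between two observed scores are filled.

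**Endpoint and population.** Under SAP 8.1, a subject's ANSS1-4 "is calculated as the mean of these daily NSS across study Days 1 to 4". No minimum number of days is given. The mITT population (SAP 4.4.2) takes subjects who "received at least one dose of study medication and have at least one post-baseline efficacy assessment".

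**Other medication.** Protocol 9.2.5 says that the primary analysis "will use the recorded cold symptom scores, irrespective of other cough/cold medication usage". Protocol 3.2, item A, says of subjects who use medication that could interfere with interpretation that "they will be discontinued from the study". Protocol 4.5 instead stops study treatment, after more than one dose of a disallowed medication.

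**Dropout analyses.** SAP 8.1.3 and Appendix D plan last observation carried forward (LOCF) and control-based imputation on a condition: "In the event that more than 10% of subjects do not complete the first 4 days of treatment", or if dropout differs between the groups. No size or test defines that difference.

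**The concern.** The plan treats stopping treatment as the end of data collection, although the subject already holds the diary and the endpoint needs only four days of it. A subject lost before the end of Day 4 is summarized over fewer days than the others but counts the same in the ANCOVA. The SAP foresees the case: Appendix C lists a subject with no doses or self-assessments after Day 1, and classes it as a non-significant deviation.

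The loss is plausibly related to outcome. Subjects with worse colds have more reason to take other medication, and Protocol 3.2 and 4.5 make some of that use a route off treatment or out of the study. Tolerability of the spray could be another reason to stop. If early loss differs by arm and symptoms change over Days 1 to 4, the primary comparison is biased. The analysis that would show how far depends on one threshold that may not be reached and on one word left to judgement.

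**Working it through.** **Inputs from the documents.** 170 subjects, 85 per arm (Protocol 9.1, SAP 4.2). Trigger of more than 10% not completing Days 1 to 4 (SAP 8.1.3). Effectiveness criterion of a mean at least 17% below placebo (Protocol 9.2.3). The nasal symptom score (NSS) sums three symptoms scored 0 to 3, so it runs from 0 to 9. There is no planning figure to reproduce: 170 is justified by the size of similar studies, with no power, SD or dropout rate attached.

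**Assumed input.** The documents give no daily NSS. Take NSS on day d as 5 − f(d − 1), with f from 0.2 to 0.8 points per day.

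**1. Scores behind one ANSS1-4.** Assessments precede doses and the baseline is excluded. Day 1 therefore yields at most 3 scores (four-dose stratum) or 2 (three-dose stratum). A completer has 3 + 12 = 15 or 2 + 12 = 14.

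**2. Overstatement per subject.** The four-day mean is 5 − 1.5f. A subject with Day 1 only scores 5, an excess of 1.5f. A subject with Days 1 and 2 only scores 5 − 0.5f, an excess of f.

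| f | Four-day mean | Day 1 only: excess | Days 1-2 only: excess |
|---|---|---|---|
| 0.2 | 4.7 | 0.3 (6.4%) | 0.2 (4.3%) |
| 0.4 | 4.4 | 0.6 (13.6%) | 0.4 (9.1%) |
| 0.6 | 4.1 | 0.9 (22.0%) | 0.6 (14.6%) |
| 0.8 | 3.8 | 1.2 (31.6%) | 0.8 (21.1%) |

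With f = 0 the excess is zero. It is also zero for a Day 1-only subject on an assumed course of 4.25, 4.75, 4.25, 3.75, which peaks on Day 2 and has a mean of 4.25.

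**3. Between-arm bias.** Bias = (difference in number of early dropouts / 85) × excess. With 17 dropouts, all after Day 1:

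- Balanced: 0.
- 5 v 12: 7/85 = 0.082. Times 0.3 this is 0.025; times 1.2 it is 0.099. Fisher's exact p for this split is 0.12, so it might well not be called differential.

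For scale, 17% of the four-day mean is 0.17 × 4.7 = 0.80 at the slow fall and 0.17 × 3.8 = 0.65 at the fast one. The bias is then about 3% (0.025/0.80) to 15% (0.099/0.65) of the target effect. More placebo dropouts favour 1146A; more active dropouts count against it.

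**4. The 10% trigger.** 17/170 is exactly 10.0% and does not fire it; 18/170 = 10.6% does. With X binomial (170, p), P(X ≥ 18) is:

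| True Days 1-4 dropout | Chance that the trigger fires |
|---|---|
| 5% | 0.2% |
| 8% | 13.6% |
| 10% | 43.6% |
| 12% | 74.8% |

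**5. What LOCF would show.** For a Day 1-only subject, LOCF puts 5 on Days 2 to 4. The mean is 5 and the excess is again 1.5f, so on a falling course LOCF repeats the problem. Control-based imputation does not carry the early score forward.

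**6. Analyses that always run.** The reset of scores within 4 hours of other medication (SAP 8.1.3, Appendix D part A) does not model scores after dropout. The per-protocol analysis (SAP 4.4.4) removes most early dropouts through its missed-dose and missed-assessment rules. The observed-case analysis (SAP 8.1.4), itself conditional on more than 20% missing, leaves the days after dropout empty.

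**The case against.** Much can be said for the plan. The two triggers are joined by *or*, so the lack of a threshold leaves room to run the analyses on a small imbalance as well as to skip them. Protocol 9.3.3 also allows further missing-data analyses after blind review. Only loss before the end of Day 4 matters, and balanced loss does no harm by this route. All of that stands, and it keeps the point modest.

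It also rules out several stronger readings that a reader might infer:

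- *Seventeen subjects could be lost from one arm with no sensitivity analysis.* The arm shift would be 17/85 × 0.3 to 1.2 = 0.06 to 0.24 points, but 17 v 0 is differential on any reading, so the dropout analyses would run.
- *Scores after other medication will not exist.* Protocol 3.2, item F, allows occasional acetaminophen, and Protocol 4.5 stops treatment only after more than one disallowed dose. Those users can stay and keep scoring.
- *Nothing at all is recorded after stopping.* The early-termination visit includes a diary self-assessment in the Schedule of Events, so one later score may exist. The plan does not say whether it counts in ANSS1-4.
- *The early days are the worse ones.* Protocol 3.4 places the worst symptoms within four days of onset, and entry is allowed up to 72 hours after onset. That makes a fall over study Days 1 to 4 plausible for many subjects, but not established. If people leave because they are worsening, a shortened average could understate.

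What survives is that the data are not collected, the endpoint rule accepts a short average, and none of the analyses certain to run models the missing days.

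**Conclusion.** The point holds as a design weakness with a cheap remedy. It is not evidence that the primary result will be wrong. Discharge on stopping, no imputation after dropout, no minimum number of days and the one-score entry rule are all in the text. Together they let a subject lost before the end of Day 4 enter the primary analysis on a shortened average.

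The size rests on the assumed symptom course: 0.3 to 1.2 points for a Day 1-only subject at falls of 0.2 to 0.8 per day, and zero if the course is flat. Between arms it needs unequal loss. About 0.02 to 0.10 points for a 5 v 12 split is a fair illustration of what could go untested. The change should be made because scores not collected cannot be recovered at analysis, and because the decision to run the relevant check should not turn on an undefined word.

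**What to change.** 1. **Protocol 3.1 and 6.4.9** (and the matching synopsis and SAP 3.1 text): state that a subject who stops study treatment without withdrawing consent keeps the e-diary and completes the scheduled symptom assessments through at least Day 4, preferably Day 8. Use those scores in the primary mITT analysis. Say whether an early-termination score counts in ANSS1-4.
2. **SAP 8.1.3 and Appendix D** (with Protocol 9.2.5): remove the 10% and differential-dropout conditions, so that the control-based imputation always runs. LOCF can be optional, since it repeats the early score.
3. **Protocol 3.2, item A, and Protocol 4.5:** reconcile whether users of interfering or disallowed medication leave the study or only the treatment. That decides who becomes a dropout, and so how far the primary analysis can use scores regardless of other medication. Which rule should apply is for the sponsor to decide.

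The cost is a short protocol amendment, some SAP wording, a few extra diary days for those who stop, and one already specified analysis that always runs.
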